7.2.3 INCB7839 Dose Modification/Interruptions

Refer to section 7.2.1 for prevention and management of thromboembolic complications.

With activation of the Phase II extension in April 2016, both dose reductions and dose interruptions are permitted in individual patients at the discretion of the treating physician if the 300 mg bid dose is not well tolerated.

Dose reductions will follow the phase I dose levels (i.e. 300 mg bid reduced 200 mg bid reduced 100 mg bid).

Dose interruptions of up to 14 days are permitted, restarting with or without a dose reduction.

General Guidelines:

Grade 1 and 2 adverse events will be treated as medically appropriate and the INCB7839 dose may be reduced by one phase I dose level (i.e. 300 mg bid may be reduced to 200 mg bid).

INCB7839 administration should be interrupted in the event of a CTCAE v4 **grade 3 or 4 treatment related toxicity** despite best medical support, until resolution to grade 1 or better. The patient may be restarted on INCB7839 at 1 dose level lower (i.e. 300 mg reduced to 200 mg bid).

Skipped doses will not be made up.

In general a patient would be taken off treatment if any of the following occurs:

- a treatment break is for more than 14 days
- the patient is unable to tolerate INCB7839 at 100 mg bid
- if the toxicity recurs (\geq grade 3) despite a dose reduction

Note: any treatment related grade 4 or 5 event may count toward the study's early stopping rules per section 13.5.

7.3 Duration of INCB7839

Patients will take INCB7839 twice a day beginning with the 2nd dose of rituximab and continuing for 90 days (+/- 3 days) unless:

- consent is withdrawn
- patient refuses INCB7839 or is non-compliant
- more than 14 days pass without dosing (regardless of reason), the patient is unable tolerate INCB7839 at the 100 mg bid level or a toxicity recurs (\geq grade 3) after a dose reduction
- disease progression
- unacceptable toxicity
- in the treating physician's medical judgment, continuing with INCB7839 is not in the best interest of the patient's health or well-being

During the extension phase, patients receiving less than 10 weeks of INCB7839 or less than 2 doses of rituximab for reasons other than toxicity will be replaced.

7.4 Duration of Study Participation

Active study participation will end 1 week after the last dose of INCB7839 unless there is ongoing treatment related toxicity, which will be treated as medically appropriate with follow-up until toxicity resolves to grade 1 or better or is stable for 3 months.

Patients will be seen at 6, 9 and 12 months post-transplant as part of the standard of care follow-up with information regarding disease status and survival recorded for this study unless one of the following occurs:

- consent is withdrawn
- patient is unevaluable – if a patient is not evaluable, follow only until the resolution or stabilization of treatment related toxicity

8 Schedule of Patient Activities

For patient convenience and unnecessary clinic visits; some flexibility is permitted in scheduling study related visits and activities. Through the day 22 visit a window of ± 3 days is permitted. A window of ± 7 days is permitted for the 3rd dose of rituximab. After day 22, visits will coordinate with BMT anniversary visits whenever feasible; however a window of ± 7 days is permitted for any study visits not linked to a BMT anniversary visit. After the end of treatment visit, disease and survival status will be obtained from the BMT database.

8.1 Standard of Care

Study Time Point	Screening (any time between day +28 and +60))	Day 1 ¹	Day 8	2- 4 days after 2 nd rituximab dose (refer to 8.2)	Day 15	Day 22	Day 36	Day 50	Day 78	End Of Treatment Visit Day 105	F/U for Disease and Survival Status ³
Consent	X										
Medical History	X				X	X	X	X	X	X	
Physical Exam	X				X	X	X	X	X	X	
Height	X										
Weight		X	X					X		X	
Review of transplant related side effects	X										
Karnofsky PS	X				X	X				X	
CBC/diff/plt	X	X	X		X	X	X	X	X	X	
Comprehensive Metabolic panel	X	X	X		X	X	X	X	X	X	
Pregnancy test if applicable	X										
Disease Evaluation ²	X								X		X ³
Rituximab		X	X					X			

1 – day 1 may occur anytime between day 28 and day 75 post-transplant

2 – disease evaluations are the results of the transplant related follow-ups at approximately day +28 and day +100 post-transplant

3 – follow-up after the final treatment visit is linked to transplanted related milestones and/or standard of care visits – information for this study will be obtained from routine data collected by the BMT database

8.2 Research Related Procedures and Activities

Study Time Point	prior to 1 st dose of rituximab	Day 8 prior to 2 nd dose of rituximab	2-4 days post 2 nd dose of rituximab	Day 15	Day 22	Day 36	Day 64 and Day 92 ³	Day 78	Day 99 (last dose of drug) ²	Day 105 ⁴
PT/INR	X									X
D-dimer refer section 7.2.1	X				X					X
Review of drug log (AEs)/ tablet count		X				X	X ³	X		X
Monitor for stopping rules (phase II)	Per section 13.5 by 4 months post-transplant									
five 10 ml heparin (green top) tubes, one 10 ml serum (red top) tube	X	X	X		X			X		X
INCB7839	begin assigned dose bid daily for 90 days (+/-3 days)									

1 – all blood samples go to TTL

2- day 99 is not a scheduled clinic visit but instead the time point where the patient discontinues drug

3- at day 64 and 92 – research nurse or designee will contact the patient; visits are not required.

4 - or 1 week after the last dose of INCB7839 if stopped earlier

All samples go to the Masonic Cancer Center's Translational Therapy Lab (TTL).

Research sample collection is tied to the clinical care schedule of events and their associated window for performance. Therefore, if a clinical time point does not occur or is altered, the research related time point will be adjusted (or eliminated) as appropriate.

It is recognized that with novel therapies as used in this study, the timing of protocol directed research samples may miss important patient specific events. For this reason, up to 3 extra samples for a total of 180 ml of blood may be drawn at additional time points that are not specified above.

9 Study Drugs

9.1 INCB7839

Classification: ADAM Inhibitor

Dosage and Administration Schedule: For the purposes of the study, INCB7839 will be administered twice daily for 90 days beginning with the 2nd dose of rituximab

Dose Forms and Strengths: 100 mg tablets

Availability: For the purposes of this study INCB7839 will be provided by the manufacturing, Incyte Corporation packaged in HDPE bottles. All bottles of Incyte investigational product contain the following language: "Caution: New Drug—Limited by Federal Law to Investigational Use".

INCB7839 Expected Side Effects: In healthy volunteer studies, mild nausea, headache, dizziness, and tinnitus have been noted which may possibly be due to administration of INCB7839. One patient with a history of hot flashes experienced a hot flash of moderate intensity. One subject experienced a SAE of DVT that was possibly related to drug exposure; this patient was subsequently found to have a deficiency of antithrombin-III.

In studies of cancer patients, INCB7839 has generally shown to be tolerated at doses up to 500 mg bid. Adverse events most frequently occurring in patients receiving INCB7839 include nausea or vomiting, anorexia, fatigue, dyspnea, constipation, pyrexia, cough, asthenia, and headache.

Thrombotic events, primarily venous thromboses, have been observed at a higher than expected rate for the study population; thrombosis is defined as the dose-limiting toxicity. Investigators should discuss the risk with their patients, and maintain a high level of vigilance for signs of possible thromboembolism. Prophylactic anticoagulation is used as a precaution; it is not currently known how effective these measures are in reducing the risk of thromboembolism.

Please refer to the Investigator Brochure for additional information.

Contraindications: INCB7839 is contraindicated in subjects with clinically significant hypersensitivity to any component of its formulation.

9.2 Rituximab

Trade name: Rituxan

Classification: Monoclonal Antibody, Antineoplastic Agent

Category: Biological Response Modifier Agent

Dosage and Administration Schedule: For the purposes of the study, Rituximab 375 mg/m² IV administered per institutional guidelines within 4 weeks of the day 28 post-transplant re-assessment and again 2 and 8 weeks later.

Dose Forms and Strengths: 100 mg/10 mL and 500 mg/50 mL solution in a single-use vial

Availability: Available by prescription

Warnings And Precautions:

- Tumor lysis syndrome – administer prophylaxis and monitor renal function
- PML - monitor neurologic function. Discontinue rituximab
- Hepatitis B reactivation with fulminant hepatitis, sometimes fatal – screen high risk patients and monitor HBV carriers during and several months after therapy. Discontinue Rituxan if reactivation occurs.
- Cardiac arrhythmias and angina can occur and can be life threatening. Monitor patients with these conditions closely.
- Bowel obstruction and perforation - evaluate complaints of abdominal pain.
- Do not administer live virus vaccines prior to or during Rituxan.
- Monitor CBC at regular intervals for severe cytopenias
- Pregnancy Category C

10 Adverse Event Reporting

Toxicity and adverse events will be classified according to NCI's Common Terminology Criteria for Adverse Events V 4.0 (CTCAE). A copy of the CTCAE can be downloaded from the CTEP home page (http://ctep.cancer.gov/protocolDevelopment/electronic_applications/ctc.htm#ctc40).

10.1 Definitions

Note: throughout this section the generic term “drug” refers to the INCB7839 and rituximab.

The following definitions are based on the Code of Federal Regulations Title 21 Part 312.32 (21CFR312.32(a)).

Adverse Event: Any untoward medical occurrence associated with the use of a drug in humans, whether or not considered drug related.

Suspected Adverse Reaction: Any adverse event for which there is a reasonable possibility that the drug caused the adverse event.

Treatment-Emergent Adverse Event: Any event not present prior to the initiation of the treatment or any event already present that worsens in either intensity or frequency following exposure to the treatment. A treatment emergent AE refers to an event temporally related to the study treatment regardless of the causality assessment by the investigator.

Life-Threatening Adverse Event Or Life-Threatening Suspected Adverse Reaction: An adverse event or suspected adverse reaction is considered “life-threatening” if, in the view of either the investigator or sponsor, its occurrence places the patient or subject at immediate risk of death.

Serious Adverse Event Or Serious Suspected Adverse Reaction: An adverse event or suspected adverse reaction is considered “serious” if, in the view of either the investigator or sponsor, it results in any of the following outcomes:

- Death
- A life-threatening adverse experience
- Inpatient hospitalization or prolongation of existing hospitalization
- A persistent or significant incapacity or substantial disruption of the ability to conduct normal life functions
- A congenital anomaly/birth defect.

- Important medical events that may not result in death, be life-threatening, or require hospitalization may be considered serious when, based upon appropriate medical judgment, they may jeopardize the patient or subject and may require medical or surgical intervention to prevent one of the outcomes listed in this definition

If either the IND sponsor or the investigator believes the event is life-threatening or serious, the event must be evaluated by the sponsor for expedited reporting (21CFR 312.32(a)).

Unexpected adverse event or unexpected suspected adverse reaction: An adverse event or suspected adverse reaction is considered “unexpected” if it is not listed in the investigator brochure or is not listed at the specificity or severity that has been observed; or, if an investigator brochure is not required or available, is not consistent with the risk information described in the general investigational plan or elsewhere in the current application, as amended. Thus, adverse events that occur as part of the disease process or underlying medical conditions are considered unexpected; however, they will not be reportable per section 10.3.

Unanticipated (unexpected) problems/events as defined by the University Of Minnesota IRB are those that are not already described as potential risks in the consent form, not listed in the Investigator’s Brochure or not part of an underlying disease.

Note: The major discord between the FDA and IRB definitions is whether or not the underlying disease is included when considering expectedness.

The following definitions are from the Masonic Cancer Center’s Standard Operating Procedure (SOP) Deviation Reporting:

Major Deviation: A deviation or violation that impacts the risks and benefits of the research; may impact subject safety, affect the integrity of research data and/or affect a subject’s willingness to participate in the research. Deviations that place a subject at risk, but do not result in harm are considered to be major deviations.

Minor Deviation: A deviation or violation that does not impact subject safety, compromise the integrity of research data and/or affect a subject’s willingness to participate in the research.

Expedited (Rapid) Reporting: Certain events may require rapid notification to entities providing patient safety oversight (e.g. IRB, FDA) as

detailed in section 10.3. For the IRB this is 5 business days. For studies under an IND, it is 7 or 15 calendar days.

10.2 Adverse Event Documentation

For the purposes of this study adverse event monitoring will begin with the 1st dose of rituximab. The adverse events associated with rituximab in the post-transplant setting are well characterized and expected events will not be documented. However, any event felt at least possibly related to rituximab and meets the criteria for expedited reporting per section 10.3 will be documented.

Adverse event documentation for INCB7839 will begin with the 1st dose. Events will be recorded onto study specific case report forms based on the following table:

Relation to INCB7839	Grade 1	Grade 2		Grade 3		Grade 4 and 5
	Expected or Unexpected	Expected	Unexpected	Expected	Unexpected	Expected or Unexpected
Unrelated	Not required	Not required	Not required	Not required	Required	Required
Possible Probable Definite Unlikely	Not required	Required	Required	Required	Required	Required

After the final treatment visit approximately 1 week after the discontinuation of INCB7839 formal AE documentation will end, however; the investigator must report upon knowledge any study treatment related event meeting the criteria for expedited reporting in section 10.3 or events related to the study stopping rules.

During the Fast-Track Design: any grade 2 or greater treatment emergent adverse event during the 1st 14 days of INCB7839

Dose Limiting Toxicity: The following events within the 1st 14 days of INCB7839 meet the definition of dose limiting toxicity during the dose escalation phase component and must be reported to the MCC Study Coordinator using the DLT Report Form:

- any grade 3 or greater non-hematologic, non-infectious toxicity including thromboembolic complications
- selected hematologic toxicity within the 1st 14 days of INCB7839
 - grade 4 neutropenia lasting for ≥ 7 days

- febrile neutropenia
- grade 4 thrombocytopenia lasting for ≥ 7 days despite dosing delay
- grade 3 thrombocytopenia associated with bleeding
- inability to complete at least 10 days (20 doses) of twice daily INCB7839 therapy within the 1st 14 days due to treatment related toxicity

Stopping Rule Events: The following events count toward a study stopping rule during the phase II (extension) component per section 13.5 and must be reported to the MCC Study Coordinator using the Early Stopping Rule Report Form:

- Grade 4-5 non-hematologic toxicity by 4 months post-transplant
- Grade 4-5 hematologic toxicity lasting 7 or more days by 4 months post-transplant

Events that count toward dose limiting toxicity or an early stopping rule do not necessarily constitute a serious adverse event requiring expedited reporting and should be reported as such only if they meet the criteria for expedited reporting to the IRB as defined in section 10.3.

In addition, although not always an event requiring expedited reporting, deaths with cause will be recorded in OnCore upon knowledge in the follow-up tab.

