1.2 Secondary Objectives

- To evaluate the safety and tolerability of the ADAM17 inhibitor INCB7839 in combination with rituximab
- To determine incidence of serious adverse events
- To evaluate 1 year disease-free survival
- To evaluate 1 year overall survival
- To determine time to relapse/progression

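### Section 10.2 has no rule that a serious event must be recorded because it is serious, so the secondary objective on SAE incidence can be undercounted with no safeguard

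*Combined protocol and SAP*

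**What the plan says.** Two secondary objectives in Section 1.2 depend on safety records: "To evaluate the safety and tolerability of the ADAM17 inhibitor INCB7839 in combination with rituximab" and "To determine incidence of serious adverse events". Neither is limited by grade, causality or expectedness.

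Section 10.1 defines an adverse event as "Any untoward medical occurrence associated with the use of a drug in humans, whether or not considered drug related" and notes that "throughout this section the generic term “drug” refers to the INCB7839 and rituximab". It defines serious by outcome; one qualifying outcome is "Inpatient hospitalization or prolongation of existing hospitalization".

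Section 10.2 then sets two recording rules.

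- **Rituximab.** Monitoring starts with the first rituximab dose, but "The adverse events associated with rituximab in the post-transplant setting are well characterized and expected events will not be documented". The exception is an event at least possibly related to rituximab that also meets the expedited criteria of Section 10.3.
- **INCB7839.** From its first dose, "Events will be recorded onto study specific case report forms based on the following table". The table has two rows (unrelated; unlikely, possible, probable or definite) and six columns formed from grade and expectedness.

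Section 13.4 says only that safety will be summarized by frequencies and proportions. It names no other source for the SAE count.

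**The concern.** The objective counts events by outcome, while the CRF rule selects them by grade, expectedness and relation to INCB7839. A hospitalization can be an SAE under Section 10.1 and still fall in a cell of the Section 10.2 table where no record is required. The count then depends partly on whether an investigator, in an open-label single-arm trial, judges an event unrelated or merely unlikely to be related. An analyst working from the CRFs could not tell how many SAEs were left out, because an absent record looks the same as an absent event.

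**Working it through.** No stated figure needs reproducing. The check sets the sections side by side.

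**Step 1: the CRF table in Section 10.2.**

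| Relation to INCB7839 | G1 | G2 expected | G2 unexpected | G3 expected | G3 unexpected | G4-5 |
|---|---|---|---|---|---|---|
| Unrelated | no | no | no | no | yes | yes |
| Unlikely or more | no | yes | yes | yes | yes | yes |

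Here yes means that a record is required. The count of no cells is 4 + 1 = 5 of 12, and none changes if the event is serious. This counts cells; it says nothing about the share of SAEs that fall in them.

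**Step 2: the week before INCB7839.** INCB7839 starts with the second rituximab dose (Section 7.2), which is 1 week ± 3 days after the first (Section 7.1), so the interval is 7 − 3 = 4 to 7 + 3 = 10 days. The table does not yet apply. An expected rituximab reaction that leads to admission needs a record only if it meets the Section 10.3 criteria.

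**Step 3: do other sections close the gap?**

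- Section 10.1 has the sponsor evaluate serious events for expedited reporting. That is not a rule to record them.
- The FDA expedited criteria in Section 10.3 turn on an unexpected event, an increased rate, or findings from other sources. The unexpected-event criteria exclude events clearly unrelated to INCB7839. Other events go to the annual report in summary form.
- The IRB criteria printed in Section 10.3 are unanticipated death, new or increased risk, and events that force a protocol or consent change.
- The SAE Coordinator's own row covers dose-limiting and stopping-rule events, and Section 11.3 refers back to Section 10.3.

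None of these requires every SAE to be recorded.

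**Step 4: what is captured anyway.** After INCB7839 starts, the table requires all grade 4-5 events, all unexpected grade 3 events, and every grade 2 or higher event rated at least unlikely related. Section 10.1 classes events from the disease or an underlying condition as unexpected, so unrelated grade 3 events of that kind are recorded. Section 10.2 has deaths with cause entered in OnCore, and dose-limiting and stopping-rule events have their own forms.

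**Step 5: what remains.** SAEs with no required record are:

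- (a) grade 1, any relation;
- (b) grade 2, judged unrelated;
- (c) grade 3, expected and judged unrelated;
- (d) expected rituximab events before INCB7839 that miss the expedited criteria.

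An example of (c): Section 9.1 lists pyrexia among the frequent INCB7839 events. If the brochure lists it at the observed severity (an assumption; the brochure is not supplied), a phase II admission for grade 3 pyrexia judged unrelated needs no CRF entry. The stopping rules in Section 13.5 count only grade 4-5, so they would not pick it up.

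**Step 6: an internal conflict.** Rituximab continues after INCB7839 starts; the third dose is at week 7. An expected grade 4 rituximab reaction then is excluded by the rituximab sentence and required by the table.

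**Step 7: scale, under assumed rates only.** Let q be the chance that a patient has at least one SAE in categories (a) to (d), with patients independent and no voluntary recording. The chance of missing at least one such patient's event is 1 − (1 − q)^n. Section 13.2 gives n = 18 at the phase II dose, 12 of them in the extension.

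| q (assumed) | n = 18 | n × q | n = 12 | n × q |
|---|---|---|---|---|
| 2% | 30% | 0.36 | 22% | 0.24 |
| 5% | 60% | 0.9 | 46% | 0.6 |
| 10% | 85% | 1.8 | 72% | 1.2 |
| 20% | 98% | 3.6 | 93% | 2.4 |

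The documents support no particular q. Incidence counted per patient falls only when the patient has no other recorded SAE.

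**The case against.** The strongest reply is that the filter is deliberate and mostly safe. Unlikely events share a row with related ones, so from grade 2 upward only a flat judgement of unrelated removes an event. The revision history shows that this followed an FDA comment in March 2014. Disease and comorbidity events count as unexpected, which shrinks the grade 3 gap to brochure-listed events ruled wholly unrelated. SAE incidence is descriptive and drives no decision, since dose-limiting toxicity and the stopping rules use graded events with their own forms. All of this stands, and it limits the point without answering it: no rule makes the SAE count complete.

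A reader might go further in four ways that the documents do not support.

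- **The count will be low.** A record that is not required is not forbidden, and admissions should be in the charts of this single institution. The supported statement is that the count can be low.
- **A rituximab-attributed event is by definition unrelated to INCB7839.** No section says so. During combined dosing it can be rated unlikely or possible, and is then recorded from grade 2. If judged unrelated, a grade 3 reaction absent from the brochure would count as unexpected and fall in a required cell.
- **The week before INCB7839 hides a combination effect.** No combination effect can appear before INCB7839 is taken.
- **The IRB route is fully known.** Section 10.3 refers to the IRB website for complete details, so only the printed criteria can be assessed.

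**Conclusion.** The point holds in a limited form. Section 10.2 has no override for seriousness, so the SAE incidence named in Section 1.2 can be undercounted in categories (a) to (d), and nothing in the plan would reveal it. The direction is downward, and for (b) and (c) it depends on attribution without blinding. The size cannot be estimated, because the documents give no SAE rate and no split by grade, expectedness or relation; the table of assumed q shows scale only. A specific percentage fall in SAE incidence would be invention.

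The conclusion assumes that sites record what is required and no more, and that no CRF instruction outside these documents adds SAEs. It does not extend to the stopping rules or the dose-limiting toxicity assessment. Separately, the rituximab sentence and the required cells of the table conflict once INCB7839 has started and must be reconciled. This is a cheap improvement to a secondary objective that should be made; it does not threaten the primary analysis.

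**What to change.** Add one rule to Section 10.2: every event that meets the Section 10.1 definition of serious, from the first rituximab dose to the final treatment visit, goes on the CRF whatever its grade, expectedness or attribution. Record attribution to INCB7839 and to rituximab separately. Keep the grade table for non-serious events, and reword the rituximab sentence so that it no longer contradicts the table.

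In Section 13.4, compute SAE incidence from these records, state that window, and name the denominator, including whether replaced patients stay in it. All patients who receive the first rituximab dose would match the window. If the sponsor prefers not to collect these events, the alternative is to narrow the Section 1.2 objective to the SAEs that are collected and report it under that label.

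The cost is a short amendment, one CRF rule and a few more entries per patient at one institution. For patients already treated, the omitted SAEs would have to be looked up in the charts.

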13.5 Early Study Stopping Rules – Phase II Component

For phase II component, early stopping rules will be used to monitor the excess toxicity for the additional 12 patients. Stopping rules were developed using Pocock stopping boundaries.¹⁷

Grade 4-5 non-hematologic toxicity by 4 months

Stopping rules were developed for excessive Grade 4-5 non-hematologic toxicity. The goal is to construct a boundary based on toxicity such that the probability of early stopping is at most 10% if the toxicity rate is equal to 10% and our sample size is 12 in phase II component. Given these parameters, the upper stopping boundary for toxicity is 2 events out of 4 patients, 3 out of 10, and 4 at any time. If the true toxicity rate is as high as 40% then the chance of early stopping is 87% and the expected sample size is 6.0.

Grade 4-5 hematologic toxicity lasting for ≥ 7 days by 4 months

Stopping rules were developed for excessive Grade 4-5 hematologic toxicity lasting for ≥ 7 days. The goal is to construct a boundary based on toxicity such that the probability of early stopping is at most 10% if the toxicity rate is equal to 30% and our sample size is 12 in phase II component. Given these parameters, the upper stopping boundary for toxicity is 3 events out of 3 patients, 4 out of 5, 5 out of 8, 6 out of 10, and 7 at any time. If the true toxicity rate is as high as 60% then then chance of early stopping is 75% and the expected sample size is 7.7.

14 Conduct of the Study

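### The phase II stopping rules count events only to 4 months post-transplant, so up to about 57% of a late starter's INCB7839 course lies outside the count

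*Combined protocol and SAP*

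**What the plan says.** Section 10.2 lists two kinds of event that count toward stopping the phase II component. The first is "Grade 4-5 non-hematologic toxicity by 4 months post-transplant". The second is grade 4-5 hematologic toxicity lasting at least 7 days, with the same time limit. The schedule in section 8.2 tells staff to monitor for the rules "Per section 13.5 by 4 months post-transplant".

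Both sections defer to 13.5, which heads its first rule "Grade 4-5 non-hematologic toxicity by 4 months" and names no starting point; the hematologic heading does the same. The non-hematologic boundary is built so that "the probability of early stopping is at most 10% if the toxicity rate is equal to 10" per cent. It stops at two events in the first 4 patients, three in the first 10, or four at any point. Its sensitivity is given as "If the true toxicity rate is as high as 40% then the chance of early stopping is 87" per cent. The hematologic rule is designed around 30% and stops with 75% chance at 60%.

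INCB7839 starts at the second rituximab dose, one week after the first, and lasts 90 days, plus or minus 3 (sections 7.1 to 7.3). Sections 4, 5.3, 6 and 8.1 (footnote 1) allow the first rituximab dose up to day 75 post-transplant.

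**The concern.** The toxicity cutoff is fixed to the transplant date, but drug exposure moves with the start day. A patient who starts late is followed by the formal rule for only part of the course, yet enters the denominator as one complete patient. A late grade 4-5 event in that patient would not move the trial toward its boundary.

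This is the only numerical study-stopping trigger in phase II. If the reader takes the 40% and 60% rates as rates over the drug course, which is the quantity of interest for a 90-day drug, the stated chances of stopping are too high. The missing origin in 13.5 adds a second reading: 4 months from first treatment would cover nominal dosing in full, but no section says that.

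**Working it through.** **1. Reproducing section 13.5.** Exact binomial recursion, with the boundary checked after each of 12 patients:

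| Rule | True rate | Chance of stopping | Expected N | Plan states |
|---|---|---|---|---|
| Non-hematologic | 10% | 9.8% | 11.4 | at most 10% |
| Non-hematologic | 40% | 86.6% | 5.98 | 87%, 6.0 |
| Hematologic | 30% | 9.5% | 11.5 | at most 10% |
| Hematologic | 60% | 74.8% | 7.70 | 75%, 7.7 |

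The boundary arithmetic is right for a rate within the counted window.

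**2. Drug days outside the count.** Let s be the post-transplant day of the first rituximab dose. Drug starts on day s + 7 and ends on day s + 7 + 89 = s + 96. Four months is day 120 to 122. Days outside = (s + 96) − cutoff.

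| Start day s | Drug days | Days outside, of 90 | Share |
|---|---|---|---|
| 28 | 35-124 | 2-4 | 2-4% |
| 45 | 52-141 | 19-21 | 21-23% |
| 60 | 67-156 | 34-36 | 38-40% |
| 75 | 82-171 | 49-51 | 54-57% |

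The allowed windows move these figures. A day-28 starter with a 4-day gap and 87 days of drug (days 32-118) is fully covered. A day-75 starter can have 43 to 57 days outside. Section 8.2 says "day 99 is not a scheduled clinic visit but instead the time point where the patient discontinues drug". On that label the day-75 starter's last dose is on post-transplant day 75 + 98 = 173.

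**3. Effect on the chance of stopping (illustration).** The documents give neither the mix of start days nor the timing of events, so both are assumed, and all 90 days are assumed taken. With p the full-course rate and f the share of cumulative hazard falling by the cutoff, the counted rate for one patient is 1 − (1 − p)^f, averaged over start days. Example: even starts over days 28-75 and constant hazard turn 40% into 29.6-30.4% and 60% into 46.5-47.6%.

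| Even starts over | Hazard | Stop at 40% non-hematologic | Stop at 60% hematologic |
|---|---|---|---|
| Full coverage | any | 87% | 75% |
| Days 28-42 | constant | 80-82% | 64-66% |
| Days 28-42 | halves every 30 days | 85% | 71-72% |
| Days 28-60 | constant | 73-75% | 52-55% |
| Days 28-60 | halves every 30 days | 82-83% | 67-68% |
| Days 28-75 | constant | 66-68% | 41-44% |
| Days 28-75 | halves every 30 days | 79-80% | 61-63% |
| Days 28-75 | halves every 14 days | 84-85% | 71% |

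**4. The price of a longer window.** Suppose 10% and 30% are the acceptable 4-month rates. Under constant hazard and even day 28-75 starts, the matching full-course rates are about 14% and 40%. Unchanged boundaries would then stop falsely with chance 19-20% and 25-27%. With a 30-day half-life those figures are 13% and 14-15%; with constant hazard and day 28-42 starts, 12-13% and 13-14%. Boundaries re-derived for about 14% and 40%, by a constant pointwise level that also reproduces the plan's own boundaries, keep false stopping below 10%. They stop with chance 71-75% at 40% and 44-52% at 60%.

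**The case against.** No figure in 13.5 is wrong: the rules are headed as 4-month rules, and 8.2 and 10.2 supply the origin, so the sections can be read together as one window. That is fair. It leaves open whether that window suits a 90-day drug with a floating start.

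Even starts over days 28-75 are pessimistic. Section 7.1 places the first dose on or shortly after the day-28 assessment. The revision history shows that days 61-75 were opened only in February 2018, after phase II had enrolled since April 2016. This limits the size: the day 28-60 rows are the better guide for patients enrolled before that change. It does not remove the gap, since a day-60 starter still has 38-40% of drug days uncounted.

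The illustration also gives no hazard to the week before INCB7839, although under 10.2 "adverse event monitoring will begin with the 1st dose of rituximab" and events in that week could count. This affects the modelled figures, not the drug days left out.

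Other safeguards continue: recording of grade 4-5 events to the final treatment visit, expedited reporting, quarterly reports to the monitoring council, individual off-treatment rules, and the thrombosis trigger in 7.2.1, which has no 4-month limit but changes prophylaxis without stopping the study. After the final visit, 10.2 still requires reporting of treatment-related expedited events "or events related to the study stopping rules", but stopping-rule events carry the same 4-month definition. The note in 7.2.3 defers to 13.5. None of these extends the formal count.

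Finally, if the acceptable rates must rise, re-derived boundaries recover little in the worst illustrated case (71-75% and 44-52%, against 66-68% and 41-44%). That stands as a limit on the benefit.

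**Conclusion.** The point holds and should be fixed. On the nominal schedule the formal count omits 2-4% of drug days for a day-28 starter, 38-40% for a day-60 starter and 54-57% for a day-75 starter. These shares follow from the plan's own timings and need only the reading of 4 months as day 120 to 122.

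The loss in the chance of stopping depends on assumed start days and event timing. In the cases examined it ranges from 2 to 4 points (starts by day 42, 30-day half-life) to about 20 points for the non-hematologic rule and over 30 for the hematologic rule (even starts to day 75, constant hazard). Early discontinuation of INCB7839 would shrink it. The stated 87%, 75% and 10% limits remain correct for toxicity by 4 months. The gap is in the stopping count, not in adverse event recording or reporting.

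**What to change.** State one counting window in 8.2, 10.2 and 13.5: from first study treatment to the later of 4 months post-transplant and the final treatment visit, about 1 week after the last INCB7839 dose. Taking the later date loses no event that counts now, including those in patients who stop the drug early.

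In 13.5, say that the 10%/40% and 30%/60% rates refer to that window. If the acceptable rates over it are higher than 10% and 30%, re-derive the boundaries to hold the 10% early-stopping limit and report the new chance of stopping. Section 7.2.3 needs no change, since it points to 13.5.

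Separately, reconcile the passages on rituximab timing, because they set the size of the gap: day 60 in 7.1 and the 8.1 screening heading, day 75 elsewhere, and a different schedule in 9.2.

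The cost is wording, a check of the rates and possibly less sensitive boundaries. Events still count as they occur, but a day-75 starter is known to be event-free up to about 2 months later (final visit about day 178-179 instead of day 120-122). No visits are added, and grade 4-5 events are already recorded from the first INCB7839 dose to that visit. Recording between the first rituximab dose and INCB7839 stays as limited as it is now, since 10.2 leaves expected rituximab events undocumented unless they qualify for expedited reporting.
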